### **Section 5.0. Selection and Withdrawal of Subjects**

Patients experiencing myopathic pain while consuming any statin medication will be approached by one of the study investigators regarding their participation. The study will be explained to them and if they would like to participate in the study the patient will be given a consent form to review. The patient will be given the opportunity to ask any questions. After all questions have been answered and the patient appears to fully understand the study, they will be offered additional time to think about participation and go over the study material. The patient will be given the contact information for the study investigator in order to ask additional questions. After all questions are answered, and the patient has fully reviewed the consent and decides to participate, the patient will be scheduled for her first research visit at which time written consent will be obtained.

#### **5.1 Inclusion Criteria:**

Only patients meeting all the listed criteria below will be asked to participate

2. Age > 18, using an effective form of contraception (refer to section 4)
3. An indication to be on statin therapy
4. Mild to moderate myopathic pain while on a statin
5. Pt able to continue current statin

6. Serum CK level < 10 x ULN
7. Vitamin 25 OH D level <30 ng/mL (as secondary hyperparathyroidism is triggered below this level)
8. English speaking patients only
9. Myopathic pain that cannot be attributed to other medical conditions
10. Continue a statin within the CYP3A4 family
11. Competent to give informed consent
12. Vitamin D Level <30ng/mL
13. (+)Myalgia symptoms on a statin medication
14. Negative pregnancy test

### **5.2 Exclusion Criteria:**

1. Clinical diagnosis of overt vitamin D deficiency: osteomalacia, rickets, hypocalcemia, hypophosphatemia
2. Already taking Vitamin D supplements >1000 IU/day
3. Serum creatinine > 2.2 mg/dL within last 6 months
4. AST/ALT > 3 x ULN of the local reference range
5. Serum CK level > 10 x ULN
6. Systolic blood pressure <90 mmHg
7. Albumin adjusted calcium >2.55 mmol/L or <2.20 mmol/L
8. Renal osteodystrophy
9. Malabsorption syndrome
10. Metastatic malignancy
11. Transplant recipients
12. A co-existent diagnosis of renal calculi within the previous 6 months
13. A co-existent diagnosis of primary hyperparathyroidism within the previous 6 months
14. Recent therapy with corticosteroids within the previous 6 months
15. Currently consuming Digoxin, as usage increases risk of hypercalcemia
16. Lactating women (refer to section 4)

### ***5.3 Withdrawal Criteria***

Patients who are severely intolerant to their current statin therapy, meaning hydration and rest do not improve symptoms, will be asked to exit the protocol. Patients will be brought back for their exit visits outlined in Appendix G and data regarding all measurable outcomes will be taken. In addition, remainder study drug will be collected. Patient will then be referred to primary care physician for further management of vitamin D deficiency, if persistent. In regards to statin management, patients will be withdrawn from their current statin and asked to follow up with their cardiologist or primary care physician for further statin therapy management.

## **Section 6.0 Treatment of Subjects**

### *Study Drug*

The intervention under study in this trial will be ergocalciferol, vitamin D2. Of the 40 patients selected for the study, 20 will be randomized to the treatment group while the other 20 will be randomized to a placebo group. During this time they will also be encouraged to continue taking their current medication regimen and supplemental regimen as long as the cumulative Vitamin D

dose is <1000 IU/day. Vitamin D is currently not a standard medical intervention in the treatment of myopathic pain. Vitamin D, in this study, is being used to treat patients with low serum 25 OH D levels. In addition, assessing for vitamin D deficiency is not routine and there is no consensus on who should be offered therapy; therefore, since the study extends for a short period of time, it is safe for deficient patients to be randomized to the placebo arm. Furthermore, upon completion of the study, patients who were vitamin D deficient and randomized to the placebo arm will be offered therapeutic doses of vitamin D.

Currently, there is no consensus on an optimal serum 25 OH-D level in asymptomatic insufficient patients. Optimal serum goals are set based on overt symptoms of deficiency which typically occur at levels <15 ng/mL. Therefore, the current standard of care is to treat patients with high dose ergocalciferol to keep levels at least >20ng/mL but ideally >30ng/mL as secondary hyperparathyroidism is prevented at these serum concentrations. Since we are testing whether vitamin D supplementation will improve statin-related myalgias in subjects with low serum vitamin D levels, we have planned our study feasibility based on a 30ng/mL threshold. Ergocalciferol is the current standard of care for treating vitamin D deficiency. Since we are using ergocalciferol therapy to treat vitamin D deficiency, and because our trial is a pilot study, the data will not be submitted to the FDA for consideration of changing the labeled indications for ergocalciferol therapy.

## **Section 8.0        Assessment of Safety**

When the vitamin D system is overstimulated, hypercalcemia results because of increased intestinal calcium absorption and by the induction of bone re-absorption. In regards to vitamin D, hypercalcemia is the criterion for harm, because it is the agent that causes symptoms. These symptoms include nausea, dehydration, lethargy, weakness, excessive thirst, anorexia, headache, constipation, weight loss, kidney stones, arterial calcium deposits and decreased or altered urine output. However, toxicity is a rare concern with vitamin D, especially since UVB rays degrade excess vitamin D. Serum 25 OH vitamin D levels are measured approximately 2 months after initiation of high dose ergocalciferol therapy to monitor efficacy as well as toxicity. This time period is consistent with the termination of our study, where we will obtain serum calcium and 25 OH-D levels to monitor efficacy and toxicity. Furthermore, the first signs of toxicity typically do not occur until a serum 25 OH D concentration of 100-140 ng/mL (>250nmol/L), which is unlikely to be obtained at high doses prior to the 3 month monitoring period that is currently the standard of care.

Statins, although rare, can cause rhabdomyolysis. This is the main concern when patients develop myopathic pain. If serum CK levels are > 10 x ULN then the patient is toxic from statin therapy, and further therapy with statins should be discontinued. Prior to study initiation, serum CK levels will be checked to screen out patients with rhabdomyolysis in whom continuation of statins is unsafe.

## **Section 9.0.       Statistics**

Our goal sample size of enrolled patients is 40, with 20 patients in each arm. We approximate 10% of patients that we approach regarding the study will actually meet all inclusion and exclusion criteria as well as agree to the study; therefore, we estimate that we will have to approach approximately 400 patients.

**9.1 DataAnalysis for Baseline Comparability.** To establish comparability between the groups at baseline, all subjects randomized will be compared with respect to the baseline variables, including the primary and secondary outcome variables, demographics, reproductive history, risk factors, medical history, current medications, and physical exam variables. Comparisons between treatment groups will be performed using two sample t-test for normally-distributed continuous variables, Wilcoxon rank-sum test for non-normal or ordinal data, and Chi-square test for categorical variables. To evaluate whether a variable follows a normal distribution, we will use the Q-Q plot and Kolmogorov-Smirnov test.

**9.2. Data analysis to assess group difference at exit.** If there is no systematic group difference in the primary and secondary outcome variables at baseline, comparisons of these variables between the groups will be conducted using measurements taken at study exit. Two sample t-test will be used for normally-distributed variables, Wilcoxon rank-sum test for non-normal or ordinal data, and Chi-square test for categorical variables. For variables that show group differences at baseline, change scores will be used in the above analysis. Change scores will be calculated as the difference between study exit and baseline. Secondary analysis to assess group difference will be carried out using regression models to adjust for baseline covariates/factors that show group difference in 9.1. The outcomes in the regression analysis are the measurements at exit or change scores. We will use linear regression for continuous outcome variables (may be subject to transformation), logistic regression for binary variables, and proportional odds models for ordinal data.

**9.3 Study Power.** This is a pilot study, so a formal sample size calculation for statistical power is not included. Estimates of between-group difference and data variability will be used to conduct a more definitive sample size calculation for a larger study.

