#### *4.8 Course of Experiment*

During the patients routinely scheduled clinical care visit or at time of referral, the patient will be screened for study eligibility. Patients on any statin will be included. Patient must have clinically documented vitamin D level <30ng/mL within 6 months of study entry during screen. It will be determined during the screen that patients' myalgia symptoms are due to statin therapy and that patient is able to continue their current statin medication. Once all the inclusion/exclusion criteria are met, the patient is recruited into the study and scheduled for their first research visit. At research visit #1, patients will be consented for the study, have lab work drawn for safety and laboratory outcome measurements (primary and secondary outcomes), complete study surveys (SF-12 and BPI), medical history, and medication review documents. They will also undergo a physical exam where blood pressure, height, weight, vital signs, abdominal and hip circumference measurements will be taken. The patient will then be randomized to either a treatment or placebo group and given the study drug. The study will be double-blinded. The treatment group will receive Ergocalciferol therapy at 50,000IU for 8 weeks while the placebo group will receive a placebo pill that is identical in nature. Patients will be asked to continue their current statin. Once serum creatinine, calcium, urine pregnancy (child bearing women) if indicated and creatine kinase levels return, likely within the same day, patient will be given a phone call and asked to start study drug or placebo for the next 8 weeks. Patients will then be called by study investigators and/or coordinator in 1-2 weeks for a phone follow-up where tolerability of study drug will be discussed as well as discussion and documentation of any adverse events (AEs). During this phone call an exit appointment will be scheduled after completion of 8 week course of study drug vs placebo. If patient is unable to tolerate protocol an earlier exit visit will be scheduled. During the exit visit patient will undergo a repeat physical exam, complete surveys and medication review, and phlebotomy that will measure the primary outcomes, secondary outcomes, modifiable variables, and safety measurements: creatinine, calcium, and creatine kinase levels. For a temporal summary, please refer to Appendix G.

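### Section 9.2 lets a baseline comparison choose between two unadjusted tests, so the main analysis never fits an outcome's own baseline

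*Combined protocol and SAP*

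**What the plan says.** Section 9.1 compares the arms at baseline on a long list of variables that includes the outcomes themselves. Section 9.2 then uses the result to choose the main analysis, outcome by outcome. The exit-value comparison applies "If there is no systematic group difference in the primary and secondary outcome variables at baseline". Otherwise, "For variables that show group differences at baseline, change scores will be used in the above analysis". Either way the test is a two-sample t-test or Wilcoxon test (chi-square for categorical data), with no covariate. The section does not say what counts as a systematic difference.

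Regression is labelled secondary and uses "regression models to adjust for baseline covariates/factors that show group difference in 9.1". Its dependent variable is left open: "The outcomes in the regression analysis are the measurements at exit or change scores".

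Appendix G schedules the BPI, SF-12, 25-OH D, PTH, calcium and cholesterol measures at both Week 0 and Week 8. Section 9.3 gives the pilot's purpose: "Estimates of between-group difference and data variability will be used to conduct a more definitive sample size calculation for a larger study".

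**The concern.** Exit values ignore the baseline, and change scores force its slope to be 1. The data could estimate that slope, but neither main comparison does so. An outcome's own baseline enters a model only in the secondary analysis, and only when 9.1 flags it. Under randomisation most outcomes will not be flagged, so no planned model uses their Week 0 value.

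Two things are at stake. The first and larger is precision: a 40-patient pilot meant to supply an estimate of the between-group difference would set aside collected data that could sharpen it. The second is conditional bias. In a trial with a chance baseline imbalance, the exit comparison is off by slope × imbalance, and the change-score comparison by (1 − slope) × imbalance in the opposite direction. Because the threshold is undefined, the choice between them also stays open until the baseline data have been seen.

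**Working it through.** **Inputs from the documents.** 20 per arm (sections 6.0 and 9.0); outcomes measured at Week 0 and Week 8 (Appendix G).

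**Assumed, because the documents give none of these.** Two-sided 5% for the baseline and outcome tests; exit SD 1; baseline/exit SD ratio r of 1.0 or 0.7; baseline-exit correlation ρ of 0.1, 0.3, 0.5 or 0.7; normal data; true effect 0 or 0.8 SD; exit data on all 40.

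**1. The plan's own figures.** The recruitment estimate reproduces: 40 / 0.10 = 400 approached. Section 9.3 declines a power calculation, so there is no power or precision figure to reproduce.

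**2. Variance.** With exit SD 1, the per-patient variance is 1 for exit values, 1 + r² − 2ρr for change scores and 1 − ρ² after baseline adjustment. Allowing for estimation of the slope, the variance ratio of the adjusted analysis (ANCOVA) to exit values with n per arm is

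(1 − ρ²)(1 + 1/(2n − 4)) = (1 − ρ²)(1 + 1/36).

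This gives 1.017, 0.935, 0.771 and 0.524 at ρ = 0.1, 0.3, 0.5 and 0.7. Break-even is at 1 − ρ² = 36/37, so ρ = √(1/37) ≈ 0.16. To match ANCOVA with 20 per arm, an exit-value t-test needs 20/0.935, 20/0.771 and 20/0.524, or about 22, 26 and 38 per arm at ρ = 0.3, 0.5 and 0.7.

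**3. Simulating the whole rule.** Baseline t-test at 5%, then change scores or exit values, against ANCOVA. Equal SDs, effect 0.8 SD; 600,000 null and 300,000 effect trials per scenario, with half-widths from 200,000.

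| ρ | Power, plan | Power, ANCOVA | CI half-width, plan | CI half-width, ANCOVA | Type I error, plan |
|---|---|---|---|---|---|
| 0.1 | 68% | 69% | 0.65 SD | 0.64 SD | 6.2% |
| 0.3 | 69% | 72% | 0.64 SD | 0.62 SD | 5.7% |
| 0.5 | 69% | 80% | 0.64 SD | 0.56 SD | 5.0% |
| 0.7 | 71% | 93% | 0.63 SD | 0.46 SD | 4.0% |

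At r = 0.7 the plan's power is 69, 69, 70 and 71% and its type I error 5.7, 5.2, 4.5 and 3.7%; ANCOVA's power is unchanged. The plan's mean estimate is 0.80 in every scenario, so it is unbiased overall.

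**4. Bias given an imbalance.** The slope of exit on baseline is ρ/r.

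- *Not flagged, baseline p 0.05 to 0.20 (15% of trials per outcome).* The mean imbalance is about 0.5 baseline SD. Exit-value bias is (ρ/r) × 0.5r = 0.5ρ, whatever r is; simulated 0.05, 0.15, 0.25 and 0.34 SD. False positives are 5, 6, 9 and 12%.
- *Not flagged, p above 0.20 (80%).* False positives are 5, 4, 3 and 2%, at or below nominal.
- *Flagged (5%).* The mean imbalance is 0.72 baseline SD. With equal SDs, change-score bias is (1 − ρ) × 0.72 = 0.65, 0.50, 0.36 and 0.22 SD, with false positives of 30, 23, 18 and 12%. At r = 0.7 it is (1 − ρ/0.7) × 0.7 × 0.72 = 0.43, 0.29, 0.14 and 0.00 SD, with 19, 13, 7 and 5%. ANCOVA stays at 4.7 to 5.2%.

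**5. A less tidy outcome.** Assumed 0–10 integer pain score, latent mean 4.5 and SD 2, entry limited to 1–6, effect 1.6 points, Kolmogorov-Smirnov choice of t-test or Wilcoxon (12,000 trials per scenario). The SD ratio came out at 0.74 to 0.84. At observed ρ of 0.21, 0.37 and 0.55, power is 68, 74 and 80% for the plan, 70, 78 and 91% for ANCOVA, and 69, 77 and 89% for rank ANCOVA.

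**6. The input to 9.3.** For an assumed 0.5 SD difference at 80% power, n per arm = 2(1.960 + 0.842)²v / 0.5² = 62.8v, rounded up. The exit SD (v = 1) gives 63. At ρ = 0.3, 0.5 and 0.7 the change SD gives 88, 63 and 38 with equal SDs (68, 50 and 33 at r = 0.7), and the residual SD gives 58, 48 and 33. Sampling error in a variance on 38 df (0.67 to 1.66 times the estimate) already spreads the 63 over 42 to 105.

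**The case against.** **The rule is valid on average.** Over all randomisations it is unbiased, both branches estimate the same mean difference, and overall type I error is 3.7 to 6.2%. When an outcome is flagged, the secondary regression contains its baseline and gives a sound treatment estimate, whether exit or change is the dependent variable. All of this stands, and it makes the point chiefly one of precision. It does not help unflagged outcomes, and in flagged trials the sound estimate is still reported as secondary.

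**The size depends on inputs the documents do not give.** At ρ = 0.3 the gain is only 0.02 SD in half-width and about 3 points of power, and the plan sets no power target. This also stands: the direction is firm above ρ of about 0.16, the size is not.

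**The p-value bands rest on an assumed 5% threshold.** True, since none is stated. With a 20% threshold the plan's power over ρ = 0.3 to 0.7 is 66 to 76%, still below ANCOVA.

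**Restricted entry need not truncate the analysed baseline.** Section 5.1 requires "Mild to moderate myopathic pain while on a statin" without a BPI cut-off, and section 4.8 applies the 25-OH D limit to a chart value from the previous six months, not to the Week 0 draw. Any restriction is therefore indirect. Equal SDs remain doubtful rather than disproved, so both ratios are shown. The precision result hardly changes between them; the bias in flagged trials does.

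**It is a pilot, and the exit SD is a legitimate, conservative input to 9.3.** That is right for the variability estimate, where sampling error usually outweighs the branch effect. It does not answer the loss of precision in the estimated difference, which 9.3 also carries forward.

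**Conclusion.** The concern holds. The main comparison never fits an outcome's own baseline, and an undefined baseline comparison decides which of two unadjusted analyses is reported. With 20 per arm the plan's 95% CI half-width stays at 0.63 to 0.65 SD whatever the correlation. Fitting the baseline would reduce it to about 0.56 SD at ρ = 0.5 and 0.46 SD at ρ = 0.7, with little change at 0.3 and none of note at 0.1.

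Conditional bias is a lesser, real problem: at ρ = 0.5, about 0.25 SD in the 15% of trials per outcome just short of flagging. In the 5% flagged it is 0.36 SD the other way with equal SDs, or 0.14 SD at ratio 0.7. These figures rest on the assumed correlations, SD ratios, normal data and 5% baseline test. The defect does not invalidate the trial, but it should be fixed because the remedy needs no new data.

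**What to change.** Replace the switching rule in 9.2 with wording such as:

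> For each outcome measured at Week 0 (BPI, SF-12, 25-OH D, PTH, calcium, lipids), the primary analysis regresses the exit value on treatment group with that outcome's own baseline as covariate, regardless of the results in 9.1.

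- Make 9.1 descriptive only.
- State in advance which outcomes are continuous (linear regression) and which ordinal (proportional odds with the baseline as covariate). The proportional odds model estimates an odds ratio, and the figures above do not cover it.
- Keep statin tolerability by pill count as an exit comparison, because Appendix G has no Week 0 measure for it.
- In the secondary models, replace covariates picked by 9.1 with ones fixed in advance, for example the CYP3A4 medication count from section 4.5.
- Useful but less essential: a rank ANCOVA sensitivity analysis for all continuous outcomes and, for 9.3, the exit SD, residual SD and baseline-exit correlation with confidence intervals.

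The cost is SAP wording and one residual degree of freedom (37 instead of 38 with 40 exit visits). If ρ is below about 0.16 there is a slight loss against exit values (variance ratio 1.02 at ρ = 0.1).

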### *4.3 The primary outcomes of our study include:*

1. Myopathic pain
2. Quality of life
3. Vitamin 25 OH D levels
4. Statin tolerability

These will be measured used the brief pain inventory (Appendix C), the SF 12 survey (Appendix D), serum measurements, and pill counting, respectively.

*4.4 The secondary outcomes* of our study include:

1. Parathyroid hormone (PTH)
2. Calcium
3. Lipid profile

PTH and calcium levels are directly dependent on serum 25 OH D levels. In addition, lipid profiles are affected by statin compliance.

*4.5 The modifiable variable* in our study is:

Number of medications patient is taking that is metabolized by the CYP3A4 enzyme

One of the proposed mechanisms of action in statin-induced myalgia and vitamin D deficiency involve competition at the CYP3A4 enzyme. Therefore, the total amount of CYP3A4 dependent medications each patient consumes will be tabulated to assess if it confounds outcomes at the end of the study. This will be most relevant for those patients who entered the study with a statin that is metabolized utilizing the CYP3A4 enzyme (lovastatin, simvastatin, atorvastatin, rosuvastatin, fluvastatin). Because 3 of these 5 statins are available in generic formulation, they will most likely be prescribed at a higher frequency in our urban dwelling population. This will be done with a medication list review (Appendix E).

*4.6 Study population*

Recruitment of patients will occur during outpatient clinic visits and through outpatient referrals from Los Angeles-based community physicians. Community physicians will not be sharing detailed study information with patients. Our study population will consist of 40 male and female urban dwelling patients of varied ethnic origin. Although women are preferentially affected by osteoporosis and the phenomenon under study may be similar to osteomalacic myopathy, we will include men in the study for inclusiveness. All women of child bearing age included in the study must be using an effective form of contraception because statin therapy can be harmful to a growing fetus. These women are all already on statin therapy so they cannot be pregnant as per clinical care. However, to ensure patient safety, all women will undergo urine pregnancy testing at the beginning of the study. Lactating women, however, can transmit statins to children through breast milk; therefore, they will be excluded from our study.

*4.7 Safety*

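### The secondary regression in 9.2 selects covariates by chance baseline imbalance instead of a fixed prognostic list, which probably costs precision given the breadth of 9.1

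*Combined protocol and SAP*

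**What the plan says.** Section 9.1 compares the arms at baseline on a broad set of variables, "including the primary and secondary outcome variables, demographics, reproductive history, risk factors, medical history, current medications, and physical exam variables". The tests are a t-test, Wilcoxon test or Chi-square test according to variable type. No significance threshold is given and the variables are not counted.

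In section 9.2 the main comparison is an unadjusted two-sample test of exit values, or of change scores for an outcome that differs at baseline. It then adds: "Secondary analysis to assess group difference will be carried out using regression models". These models are to "adjust for baseline covariates/factors that show group difference in 9.1". No covariate is fixed in advance for them.

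Allocation is randomised, 20 per arm (sections 6.0 and 9.0). Section 4.6 says of the study population that "we will include men in the study for inclusiveness". Section 4.5 separately nominates the number of CYP3A4-metabolised medications as a possible confounder, without giving a model for it.

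**The concern.** In a properly randomised trial, a baseline difference between arms is a chance event. A rule that admits covariates because they differ therefore selects on correlation with treatment arm. That correlation inflates the variance of the treatment estimate. The rule takes no account of correlation with pain, SF-12 or 25 OH D, which is what reduces residual variance. A strong predictor that happens to be balanced stays out about 95% of the time at a 5% threshold.

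The covariate set also cannot be known until the data are in, and it may differ from what a reader would have chosen on clinical grounds. At stake are the precision and the interpretability of the regression model, which is the only one the plan specifies with covariates.

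**Working it through.** **The plan's own figures.** The only derived number in section 9.0 is the 400 patients to approach, which reproduces as 40 / 0.10 = 400. It has no bearing on this point. There is no power, alpha or effect size to reproduce.

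**Inputs from the documents.** Two arms of 20; selection by baseline test; pool as listed in 9.1.

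**Assumptions, because the documents are silent.** Selection at two-sided 5%; 5 to 40 candidate variables; independent, normally distributed candidates; three of them jointly explaining 30% of outcome variance; outcome SD of 1.

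**Step 1: cost of one selected covariate.** The critical t on 38 df is 2.024. The squared correlation of a just-selected covariate with arm is t²/(t² + 38) = 4.098/42.098 = 0.097, so r = 0.31. The variance inflation is 1 + t²/38 = 1.108, or about 11%. Averaged over all covariates that pass the threshold it is about 16%. The covariate pays for itself only if its correlation with the outcome exceeds about √(1 − 1/1.108) = 0.31 at the threshold, or √(1 − 1/1.162) = 0.37 on average.

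**Step 2: how many are selected, and the effect on precision.** With K candidates, the expected number selected is 0.05K and the chance of at least one is 1 − 0.95^K. Half-widths are means from simulation (8,000 trials per setting, with small variation between runs).

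| K | Expected selected | P(at least one) | Half-width, 9.2 rule (SD) | Half-width, unadjusted (SD) |
|---|---|---|---|---|
| 5 | 0.25 | 23% | 0.64 | 0.63 to 0.64 |
| 10 | 0.5 | 40% | 0.66 | 0.64 |
| 20 | 1.0 | 64% | 0.68 to 0.69 | 0.64 |
| 30 | 1.5 | 79% | 0.70 to 0.71 | 0.63 to 0.64 |
| 40 | 2.0 | 87% | 0.73 | 0.63 to 0.64 |

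The unadjusted value agrees with the formula 2.024 × √(2/20) = 0.640. Fixing the three prognostic covariates in advance gives about 0.56 SD at every K. If the three fixed covariates explain nothing, the fixed list gives about 0.67 SD; the rule then gives about 0.66 at K = 10 and 0.71 at K = 30.

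**Step 3: which K is realistic.** The plan does not say, but a count is possible. Outcomes give about 10: two Brief Pain Inventory and two SF-12 scores (assumed), 25 OH D, PTH, calcium, total cholesterol, LDL and HDL. The physical exam gives 6: systolic and diastolic pressure, height, weight, abdominal and hip circumference. Age, sex and ethnicity (assumed items) add 3; CYP3A4 medication count and statin type add 2. The total is 10 + 6 + 3 + 2 = 21, before reproductive history, risk factors, medical history or the 27 individual drug rows in Appendix E.

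**Step 4: the outcome's own baseline.** With 30 candidates and an assumed baseline-to-exit correlation of 0.5, the SD of the treatment estimate is 0.273 when the baseline value is always fitted, 0.315 unadjusted and 0.342 under the rule. At a correlation of 0.3 the three are 0.299, 0.311 and 0.345; at 0.7 they are 0.231, 0.317 and 0.337.

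**Step 5: Type I error.** In these simulations the rule rejects in about 3% to 5% of null trials, so there is no inflation.

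**The case against.** The strongest objection is that the loss against no adjustment depends on a pool size and prognostic strengths that the documents do not give. This stands. With 10 candidates the SD of the estimate is practically the same under the rule and unadjusted (0.314 v 0.314 with three prognostic variables). With 5 candidates explaining half the variance the rule has the smaller SD (0.30 v 0.32). Correlation among candidates also shrinks the loss: 20 variables correlated at 0.4 give half-widths of 0.650 v 0.637 SD. A reader might infer that the rule is always worse than no adjustment; the documents do not support that.

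A fixed list is not free either. If it explains nothing it is itself worse than no adjustment, and at 10 candidates it only ties with the rule. Nothing in the documents shows how strongly age, sex or baseline 25 OH D predicts pain or SF-12.

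A reader might also infer that the regression will drop the men, since 9.1 lists reproductive history. That needs three things: such an item is selected (5% of trials with one item tested, 14% with three), it is coded missing for men, and the model is fitted to complete cases. The plan states neither the coding nor the handling of missing covariates. It is a risk to close in the wording, not a stated defect.

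Finally, a reader might infer that the rule damages the sizing of the next study under 9.3. Section 9.3 does not say its estimates come from this regression, and the residual SD is essentially the same under the rule as unadjusted (about 0.98 to 0.99 v 0.99). That inference fails.

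**Conclusion.** The selection rule is a real weakness of modest size. It follows imbalance and not prognosis, each covariate selected at the threshold costs about 11% in variance unless it happens to be prognostic, and useful balanced covariates are usually omitted. With about 20 or more mostly weak candidates, which the categories in 9.1 make likely, the adjusted estimate is less precise than the unadjusted one, by roughly 0.04 to 0.10 SD in half-width for 20 to 40 independent candidates. With about 10 candidates the loss is around 0.02 SD.

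The gain from a fixed list is larger when it is well chosen (about 0.56 SD), but that figure assumes three covariates that explain 30% of the variance. All the sizes rest on an assumed 5% threshold, 20 analysed per arm and, unless stated, independent candidates. Because the analysis is secondary, the trial is a pilot without a power claim and false positives are not increased, this is an inexpensive improvement and not a threat to the trial's main comparison.

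**What to change.** In section 9.2, replace the instruction to "adjust for baseline covariates/factors that show group difference in 9.1" with a short fixed list that applies whatever 9.1 shows. The list should be the outcome's own baseline value plus a few variables thought to be prognostic, for example age, sex and baseline 25 OH D (for the 25 OH D outcome the first and last coincide). The CYP3A4 medication count that section 4.5 already nominates is another candidate; use the study-onset value recorded in Appendix E. Choose the list before unblinding.

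Keep 9.1 as a descriptive table that selects no covariates. State that every listed covariate must be defined for all patients. That excludes reproductive-history items from models that include men and removes the complete-case risk: at an assumed 30%, 50% or 70% men, restricting to women would multiply the standard error by √(40/28) = 1.20, √(40/20) = 1.41 or √(40/12) = 1.83.

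The cost is a sentence or two and no new data. The downside is one degree of freedom per listed variable: three variables that prove not to be prognostic would give a half-width of about 0.67 SD against 0.64 unadjusted.

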### *4.2 The primary aims of our study include:*

1. Assess if treatment of vitamin D deficiency improves statin-induced myopathic pain
2. Assess if treatment of vitamin D deficiency improves statin tolerance
3. Assess if treatment of vitamin D deficiency improves the quality of life in patients with statin-induced myopathic pain

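### Must Section 9.3 say how the imprecision of the pilot's treatment difference will be handled when a larger study is sized?

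*Combined protocol and SAP*

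**What the plan says.** Section 9.0 sets the size without a supporting effect or SD: "Our goal sample size of enrolled patients is 40, with 20 patients in each arm". Section 6.0 gives the same 1:1 split. Section 9.3 explains why there is no power calculation, "This is a pilot study, so a formal sample size calculation for statistical power is not included", and then says what the results will be used for: "Estimates of between-group difference and data variability will be used to conduct a more definitive sample size calculation for a larger study".

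Section 9.2 makes unadjusted tests at exit the main comparison: "Two sample t-test will be used for normally-distributed variables, Wilcoxon rank-sum test for non-normal or ordinal data, and Chi-square test for categorical variables". Change scores replace exit values only for variables that differ at baseline, and regression adjustment is secondary.

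No section mentions a confidence interval, a minimum important difference, a conservative bound or a shrinkage rule. Section 6.0 calls the trial a pilot and says its data will not go to the FDA to seek a labelling change.

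**The concern.** Section 9.3 names two inputs to the later calculation, the treatment difference and the variability, and treats them alike. Forty patients estimate an SD tolerably well and a difference poorly. Required sample size varies as one over the square of the standardised difference, so an error in the difference is magnified. If the point estimate became the target effect, and only pilots favouring vitamin D led to a larger study, that study could be several times too small or too large. The patients and resources at risk belong to the later study, not to this one.

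**Working it through.** **Inputs from the documents.** 20 per arm (Sections 6.0 and 9.0); unadjusted two-sample comparison at exit (Section 9.2). The only derived figure in Section 9.0, the number of patients to approach, reproduces: 40 / 0.10 = 400. There is no sample size calculation to reproduce.

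**Assumptions, not in the documents.** Continuous normal outcome, equal SDs, two-sided 95% confidence, all 40 patients evaluable. For the later study: two-sided 5% and 80% power.

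**Precision of the difference**, in SD units: half-width = t(0.975, 2n−2) × √(2/n).

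- 20 per arm: 2.024 × √(2/20) = 2.024 × 0.316 = 0.640
- 18 per arm: 2.032 × √(2/18) = 0.677
- 16 per arm: 2.042 × √(2/16) = 0.722
- Adjusted for the baseline value with correlation r, t(0.975, 37) × √((1−r²) × 2/20): 0.555 at r = 0.5 and 0.458 at r = 0.7

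**Precision of the SD** (chi-square, 38 df): 95% limits are 0.82 and 1.29 times the estimate. The upper one-sided 80% limit is √(38/χ²(0.2, 38)) = 1.116 times the estimate, which multiplies n by 1.116² ≈ 1.24.

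**Effect on a later sample size.** n per arm = 2(1.96 + 0.8416)²/d². This gives 63 at d = 0.5 and 175 at d = 0.3. An observed 0.5 SD has an interval of about 0.5 ± 0.64 = −0.14 to 1.14 SD. The upper limit would give 13 per arm. The lower limit, being below zero, gives no finite n.

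**Simulation.** 1,000,000 pilots per scenario, 20 per arm, power by normal approximation. Rule A uses the pilot difference and SD, and goes forward only if the difference favours vitamin D. Rule B fixes a target of 0.5 SD and takes the SD from the pilot. Rule B+ does the same with the 80% upper limit for the SD. The range of n per arm is the 10th to 90th percentile.

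| True effect | Rule | n per arm | Power below 50% | Mean power |
|---|---|---|---|---|
| 0.5 SD (63 needed) | A | 18 to 517 | 27% | 71% |
| | B | 46 to 82 | 0.3% | 79% |
| | B+ | 57 to 102 | under 0.1% | 86% |
| 0.3 SD (175 needed) | A | 28 to about 1,870 | 42% | 62% |
| | B | 46 to 82 | 93% | 39% |
| | B+ | 57 to 102 | 67% | 46% |

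At a true effect of 0.35 SD the share below 50% power is 37% under A, 51% under B and 19% under B+.

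The upper half of the table gives rule B the right answer, because its target equals the assumed truth. In the lower half the ordering reverses on the same measure. What a fixed target reliably gives is a stable n. Whether it also gives adequate power depends on how the target compares with the true effect.

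**What the text commits to.** Section 9.3 says the estimates will be used. It does not say that the difference will be the target effect, or that only favourable pilots will lead to a larger study. Rule A needs both. The two quantities that Section 9.3 names, with the sample size, are enough to compute the interval for a continuous outcome.

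**The case for a change.** The best case for a change is that Section 9.3 offers the later calculation as the trial's purpose in place of power, so it is the natural place to say how the estimates will be used. A rule written before the data are seen would guard against picking a target effect after a favourable result, and it would cost only a few words. The gap is real: nothing elsewhere in the documents fills it. The arithmetic is also right. A half-width of 0.64 SD cannot tell no effect from a very large one, and dropout would widen it.

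The need for a rule in this document does not stand. The safeguard belongs in the protocol of the study it protects, where a sample size justification will be required anyway and where the outcome and the important difference will be chosen. Barring the pilot difference as a target would also go further than the gap, since silence about imprecision can be met by giving an interval. Someone who favours the fixed target may reply that low power against an effect too small to matter is acceptable. That is fair, but it depends on an important difference that the documents do not give, and it does not show an error in this plan.

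**Conclusion.** The concern describes a true omission but not a fault in this trial. Imprecision of about ±0.64 SD (20 evaluable per arm, continuous outcome, unadjusted) is what a pilot of 40 delivers. The plan makes no claim to the contrary and does not bind the later study to the point estimate. No comparison, conclusion or patient in this trial would be affected by different wording in Section 9.3.

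The simulated contrast of 27% with 0.3% rests on a true effect equal to the fixed target, and it turns into 42% against 93% (67% with the conservative SD) when the true effect is 0.3 SD. Prescribing a fixed target is therefore a conditional trade-off, not a clear gain. The SD-unit figures apply only to normally distributed continuous outcomes; Section 9.2 also allows for ordinal and categorical ones.

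This is a gap that analysts fill sensibly: report the pilot difference with its 95% confidence interval, and let the later study's protocol allow for that interval and consider an important difference of its sponsor's choosing. No change to the plan follows.
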